8.0 Study Endpoints*

We will examine within-person changes in blood levels of estradiol, testosterone, dehydroepiandrosterone sulfate (DHEAS), and sex hormone-binding globulin (SHBG) after three weeks of one serving of white wine daily compared to levels after three weeks of one serving of white grape juice daily.

At visits 1, 2, 3, and 4, the BIDMC Clinical Research Center (CRC) nurses will obtain a fasting blood sample. Within 72 hours, Quest Diagnostics will measure hepatic function, a complete blood count, and following visits 2 and 4, they will conduct a lipid panel. On our weekly phone check-ins, we will ask about recent health events such as unscheduled hospitalizations or any symptoms that have developed since the last meeting.

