Weekly Check-In Call: The study staff will call participants once per week and ask them if they “had any reason to speak to or visit your health practitioner since we last spoke?” If the participant responds that there have been reasons to seek care, the study staff will ask for details. The study staff will also ask if “there any other changes to your health that you want us to know about?” and if the participant reports any changes, the study staff will ask for details. This information will be relayed for the safety monitor to review in the secure REDCap system. We will use the structure of the alcohol timeline follow-back survey to assess daily alcohol and grape juice intake since the prior check-in call. We will ask participants to record their daily intake on their paper diary that we gave them at Visit 1.

Weekly REDCap Survey: Participants will complete an online weekly survey through the REDCap system. If they would prefer to complete this survey by phone, a member of the study staff will conduct this survey as an interview by phone and enter the data into REDCap on the participant’s behalf. The survey also includes the short version of the Centre for Epidemiological Studies Depression Scale (CES-D 10), a Pain Intensity Scale using a visual analog scale to rate overall pain from 0 to 100, and in two of the weekly assessments, participants will complete the Pittsburgh Sleep Quality Index (PSQI) about their sleep quality over the prior month.

As indicated in the table of assessment times below, we will collect information about eligibility at the screening visit, and at visits 1, 2, 3, and 4, we will collect information about body measurements, vital signs, blood samples, and alcohol intake. In the weekly questionnaires, participants will provide information about alcohol intake, lifestyle factors, and any concerns. We will schedule blood draws for time windows of up to ± 4 days of the end of the prior washout or drinking period. If the visit is delayed for up to four days, we will ask participants to continue the protocol (washout, white wine, or white grape juice) for the additional days. Similarly, we will schedule weekly calls for up to 4 days before or 4 days after the target schedule date.

		Screening	Washout 1	Washout 1	Visit 1	Drinking Period	Drinking Period	Drinking Period	Visit 2	Washout 2	Washout 2	Visit 3	Drinking Period	Drinking Period	Drinking Period	Visit 4	# Assessments

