12.0 Provisions to Monitor the Data to Ensure the Safety of Subjects*

We will follow the NIAAA guidelines for administration of alcohol, including attention to informed consent; selecting participants that have no known increased risk of alcohol dependence; great attention to confidentiality; restriction to participants who regularly consume alcohol rather than alcohol-naïve individuals; exclusion of pregnant women; low alcohol exposure for the intervention period of 3 weeks; access to medical backup services; and compensation for participation.

[name], a practicing primary care internist, [name], an oncology internist, or an oncology internist identified by [name] will oversee data safety. They will monitor laboratory results from the scheduled visits on a real-time basis for all participants. They will ensure comprehensive monitoring and entry of all safety-related data in the REDCap electronic research management system, distinguishing between serious adverse events, non-serious adverse events, and unanticipated problems following the BIDMC's IRB guidelines. The study team will meet every month to discuss the ongoing health and safety of participants.

At all clinic visits, we will measure vital signs and body measurements. A member of the research team will call participants once per week to ask about any reasons to speak to or meet with a health practitioner and any other health changes. At all visits and on all weekly calls, we will encourage participants to contact us about any health concerns or questions.

We will also obtain lab assays for a hepatic panel, lipid panel, and complete blood count. We will discontinue enrollment and immediately refer for treatment any participant who

- Develops liver function test abnormalities greater than 2X the upper limit of normal or
- Experiences 15% change in their white blood count, hemoglobin level, or platelet count that results in values outside the normal range or
- Experiences a doubling of their triglyceride levels that results in values outside the normal range

following the three weeks of consuming white wine.

Participants who report any excess use of their assigned beverage per week will receive additional intensive surveillance by telephone, and we will discontinue enrollment if excessive alcohol use persists.

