The content of the Data and Safety Monitoring Reports will include details such as

- a. Number of participants screened, reasons potential participants excluded, the number enrolled
- b. Frequency, mean, min/max of all laboratory safety assays, e.g., elevations in liver function tests, severe neuropsychiatric disturbances, or changes in vital signs
- c. Quality and completeness of the study data: frequency of missing or erroneous data, and frequency of outliers
- d. Safety data by treatment period, including frequency of adverse events, serious adverse events, and any data that allows for comparisons of safety among alcohol and non-alcohol dietary periods, e.g., clinical laboratory data, treatment retention, and reasons for participant dropout.

- e. Individual participant data will be available for DSMB review as needed. In the assessment of serious adverse events, the DSMB will review each case, including treatment group assignment.

The DSMB will stop the trial if there is evidence of any of the following conditions:

- a. Clear evidence of harm
- b. No likelihood of demonstrating treatment benefit (futility)
- c. Overwhelming evidence of the benefit of treatment

We have no reason to anticipate that alcohol is beneficial for sex hormone levels. Rather, we are testing whether the constant use of aromatase inhibitor therapy throughout study enrollment lowers the impact of alcohol consumption on within-person changes in sex hormone levels. If the results of the lab results indicate that the low alcohol intake is harmful as defined by the DSMB, the DSMB will stop the trial.

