14.0 Risks to Subjects*

Because alcohol will only be provided for three weeks to participants, we do not anticipate any measurable or clinically meaningful increase in the potential long-

term risks related to alcohol consumption, including any measurable risk in chronic disease. The potential risks to study participants from use of alcohol for three weeks include risks related to temporary sedation (such as the use of machinery immediately after drinking), gastrointestinal upset, flushing (in cases of genetic intolerance to alcohol or use of specific medications), and a potential worsening of liver disease among people with pre-existing liver disease. In addition, alcohol is an addictive substance, although the risk of precipitating alcohol misuse among women already consuming alcohol safely is likely low. For both arms, the assigned beverage contains ~120 calories and can cause weight gain if not balanced by decreases in the caloric content of the diet.

The only other risks related to this study are procedural and include discomfort or anxiety answering questions about medical history and pain and temporary slight discoloration of the skin after blood draws.

Specifically, potential risks associated with study participation include anxiety related to completing the questionnaires, temporary discomfort and slight discoloration of the skin after blood draws, and feeling ill after drinking a serving of wine or grape juice. However, all participants will be postmenopausal women with estrogen receptor-positive (ER+) breast cancer who regularly consume alcohol, so these risks seem less likely than if we were recruiting from the general population. There is a potential risk of psychological harm due to inadvertent disclosure of medical information. However, we will record information behind a secure firewall using the REDCap system.

Completing the online questionnaires, phone check-ins and interviews could lead to the unforeseeable risk of a breach of confidentiality if someone other than the research team obtained access to the data. However, the screening and enrollment lists, lab results, interview responses, and questionnaires will all be entered and stored in the secure REDCap system with features to export de-identified datasets for analysis. The consent forms will include participant names, but the signed forms will be stored in a locked cabinet.

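### The weekly call script leaves out the symptom question that Section 8.0 promises, so mild beverage-related symptoms may be under-recorded

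*Combined protocol and SAP*

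**What the plan says.** Section 8.0 (Study Endpoints) says the weekly phone check-ins will ask about "recent health events such as unscheduled hospitalizations or any symptoms that have developed since the last meeting".

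Section 9.0 (Weekly Check-In Call) gives the wording to be used. The first item asks whether the woman "had any reason to speak to or visit your health practitioner since we last spoke". The second asks if "there any other changes to your health that you want us to know about". Details are sought only after a positive answer, and the information goes to the safety monitor.

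Section 12.0 describes the calls in the same two terms: "any reasons to speak to or meet with a health practitioner and any other health changes". The schedule of assessments in Section 9.0 lists health events, other health changes and the intake follow-back for the calls, ten times each.

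Section 14.0 names "risks related to temporary sedation (such as the use of machinery immediately after drinking), gastrointestinal upset, flushing" among the risks of three weeks of alcohol and, for either beverage, "feeling ill after drinking a serving of wine or grape juice".

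Section 12.0 also calls for an annual summary of adverse events by category and number, including anticipated non-serious ones. The monitoring board is to receive adverse-event frequencies by treatment period and "any data that allows for comparisons of safety among alcohol and non-alcohol dietary periods".

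**The concern.** The protocol describes the content of the same call in two ways, and the version staff would read aloud is the narrower one. Drowsiness after a glass of wine or a mild stomach upset seldom sends anyone to a practitioner, so the first item will rarely find it. The second item leaves it to the woman to decide whether the symptom is worth mentioning.

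What is at stake is the description of tolerability. Under Section 9.0 the safety monitor judges self-reported symptoms for severity, expectedness and relatedness, partly from the call responses. The board then sees counts by beverage period. If mild symptoms reach the record only when volunteered, a low count is hard to read. Because the women know which beverage they are drinking, their readiness to volunteer could also differ between wine and juice.

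**Working it through.** The plan states no figure on this point, so there is none to reproduce. The check compares the text, then gives an illustration of scale.

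**1. Call content in four places**
- Section 8.0: health events and any new symptoms. A general symptom question is promised.
- Section 9.0, quoted call wording: care-seeking, and other changes the woman wishes to mention. No symptom question.
- Section 12.0: the same two topics. No symptom question.
- Schedule of assessments: two matching rows plus intake. No symptom row.

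**2. Does another described instrument cover the Section 14.0 symptoms?**
- Weekly survey: CES-D-10, a pain scale, open text, and the PSQI twice. None asks about sedation after drinking, gastrointestinal upset or feeling ill after a serving.
- Visit form: body measurements, blood samples, medical history, lifestyle, alcohol intake and medication changes. None of these is a symptom item.
- Laboratory tests, weight and vital signs: these cover liver effects and weight gain, but not the symptoms above.
- Intake follow-back: covers excess drinking.
- Flushing: alcohol flushing syndrome and use of drugs contraindicated with alcohol are exclusions in Section 3.0, so this risk is largely handled at entry.

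That leaves sedation, gastrointestinal upset and feeling ill after a serving without a prompted question.

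**3. Scale of under-recording (assumed rates; the documents give none)**

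Let p be the true risk of a symptom in one three-week period and c the probability that an affected woman reports it. With 20 women (Section 23.0), expected reports are 20 × p × c, and the chance of at least one report is 1 − (1 − pc)^20.
- p = 10%, c = 100%: 2.0 expected; 1 − 0.90^20 = 88%.
- p = 10%, c = 50%: 1.0 expected; 1 − 0.95^20 = 64%.
- p = 10%, c = 25%: 0.5 expected; 1 − 0.975^20 = 40%.
- Range for p from 5% to 20%: 64% to 99% with full reporting, and 22% to 64% with c = 25%.

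**4. Scale of differential reporting (also assumed)**

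The reported wine-to-juice ratio is the true ratio multiplied by c(wine)/c(juice). Take a true risk of 20% on both beverages, with 60% reporting on wine and 30% on juice. Expected reports are 20 × 0.20 × 0.60 = 2.4 and 20 × 0.20 × 0.30 = 1.2, a ratio of 2 with no true difference. Swapping the reporting rates gives 0.5. The direction is therefore unknown.

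**The case against.** The case on the other side is substantial, and most of it stands.
- The call does put an open health question every week and follows up positive answers. There is also weekly open text, and Section 12.0 invites women to raise concerns at every visit and call. A reader might infer that mild harms go unseen. The documents support only that they may be under-recorded.
- A reader might infer that the safety monitor knows only what the calls relay. Section 9.0 says the monitor also reviews vital signs, body measurements, liver tests, blood counts and triglycerides.
- A reader might infer that the by-beverage comparison is biased by a known amount. It is not: the reporting rates above are assumptions, either direction is possible, and counts of one to four women support no inference. The call items are already scheduled identically in all phases, and no test of mild symptoms is planned.
- A checklist does not cure unblinded reporting. Reading out expected effects may prompt some reports on wine, and it cannot stop deliberate silence.
- Draft study materials were submitted separately, and Section 11.0 refers to prepared call scripts and a manual of operations. The full form may hold more than the wording in Section 9.0.

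None of this removes the mismatch between Sections 8.0 and 9.0, or supplies a described item on the three remaining symptoms.

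**Conclusion.** The point holds as a modest improvement to safety capture. The protocol promises a symptom question that its own call wording, safety section and schedule do not carry, and the described instruments do not prompt for sedation, gastrointestinal upset or feeling ill after a serving. Counts of these by category and period may therefore be too low, by an amount the documents do not let anyone estimate. The percentages shown convey scale only and rest on assumed risks and reporting probabilities. The conclusion also assumes that the wording in Section 9.0 is what staff will use. The hormone endpoints are laboratory measures, and nothing here affects their analysis.

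**What to change.** Reconcile Sections 8.0 and 9.0, and bring Section 12.0 and the schedule into line:
- Add the Section 8.0 question on any symptoms since the last contact to the weekly call script.
- Follow it with a short fixed yes/no list of the symptoms named in Section 14.0, with onset date.
- Ask both in the same words at all ten calls: two in each washout and three in each drinking period (2 + 3 + 2 + 3 = 10).
- Relay the answers to the safety monitor as call responses already are.
- Summarise them descriptively by beverage period, with a note that unblinded self-report can still differ by beverage.

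If the full call form already contains these items, it is enough to correct the text of Section 9.0.

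The cost is a few REDCap fields and about a minute per call. For 20 completers that is 20 × 10 × 1 = 200 minutes of staff time over the whole trial. The downside is that more minor symptoms will be recorded and need review. No visit, beverage assignment or endpoint changes.

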10.0 Data and Specimen Banking*

We will store the blood samples for sex hormone levels from each study visit in a -80 °C freezer at BIDMC until all participants complete the study. Only members of the study staff will have access to the specimens.

Each specimen will be labeled with a study identifier. The crosswalk file linking these subject identifiers to participants' private health information will be stored in separate computer files with password protection, and results will be presented only in aggregate.

Once the trial is complete, we will adhere to all required regulations regarding data dissemination. As outlined in the Notice of NIAAA Data-Sharing Policy for Human Subjects Grants Research Funded by the National Institute on Alcohol Abuse and Alcoholism (<https://grants.nih.gov/grants/guide/notice-files/NOT-AA-18-010.html>), NIAAA uses an established informatics infrastructure, hosted and managed by the National Institute of Mental Health (NIMH) to enable the sharing and use of data collected from human subjects. The NIMH Data Archive (<https://data-archive.nimh.nih.gov/>) stores and disseminates data from funded clinical trials, and we will work with the NDA to create a compatible data structure and appropriately tagged fields and strip all identifiers from submitted datasets. We anticipate that data submitted to the NDA will become available to the general public 2 years after the completion of the proposed K01 award, as specified by NIAAA. Because of the limited size (20 subjects, single-center) of the proposed trial, all costs associated with data submission will be subsumed by effort allocated to the Principal Investigator and by budgeted costs at the BIDMC Clinical Research Center.

11.0 Data Management* and Confidentiality

We will present descriptive statistics on the proportion of people screened who were eligible and ineligible, and the number randomized. We will describe the health characteristics and self-reported adherence of the completers and non-completers based on the available data.

We will construct linear mixed models to examine within-person changes in levels of estradiol, testosterone, DHEAS, and SHBG from grape juice to white wine, including a random subject intercept and fixed effects for treatment and sequence. We will assess the potential for a carryover effect by evaluating a cross-product term for treatment and sequence. We will use a logarithmic transformation for skewed distributions of the sex hormone levels.

We will use Markov Chain Monte Carlo (MCMC) multiple imputation. For each treatment arm, we will use the SAS “proc mi” procedure to generate 10 multiply imputed datasets that incorporate appropriate variability across the imputations. We will use the SAS “proc mianalyze” procedure to combine the results from the imputed data sets to properly reflect the uncertainty due to missing values.

Our primary analysis will use an intention-to-treat (ITT) approach, classifying participants according to their assigned treatment arms regardless of adherence to study protocol. In a sensitivity analysis, we will use a per-protocol approach in which a participant’s follow-up will be terminated at the time, if any, at which they cease to follow the protocol, and we will adjust for pre-randomization and post-randomization factors that may predict adherence.

Our primary endpoint is free estradiol (estradiol divided by SHBG). We should have excellent power to assess effects of alcohol on DHEAS but reasonable power to detect effects on estrone sulfate, although, as a pilot study with an intentional goal of training and career development, power is but one dimension on which to evaluate the merits of the trial. We have used standard formulae to estimate the minimum detectable difference for 2-period crossover trials (http://hedwig.mgh.harvard.edu/sample_size/js/js_crossover_quant.html). Using the 4-week results of a similar crossover trial of alcohol on changes in estrone sulfate and DHEAS, and using the dosage of 15 gm/day that most closely approximates the dosage proposed in this application, we can estimate the proportional changes anticipated with varying degrees of power, as shown below at a two-sided 0.05 significance level. Based upon data presented in that trial, we estimate the SD of within-person differences to be 42% for estrone sulfate and 13% for DHEAS.

Power	Minimum Detectable Difference	
	Estrone sulfate (ng/dl)	DHEAS (ng/dl)
50%	19%	6%
80%	28%	9%
90%	32%	10%

For comparison, the increases in estrone sulfate in previous trials of alcohol were 15-21% in a trial of premenopausal women and 7-22% in a trial of postmenopausal women.

The comparable effects on DHEAS were 4-7% and 5-9%. Thus, we appear to have adequate power to detect effects of the expected size from previous crossover trials. Moreover, we have particularly strong power to exclude virtually all clinically significant increases (e.g., increases of 10% or larger) in DHEAS.

Our results would also provide all necessary information to power a more definitive trial of estrone and other estrogens.

We aim to assure data quality and protect the confidentiality of participant data. We will keep all electronic data behind secure firewalls and all paper forms in locked files accessible by authorized personnel only. Subject identifiers will be stored in separate computer files with password protection, and results will be presented only in aggregate. We will use REDCap (Research Electronic Data Capture) tools hosted at BIDMC. REDCap is a secure, web-based application designed to support data capture for research studies. REDCap provides advanced de-identification options that can be used when exporting data, such as removing known identifier fields, removing invalidated text fields, notes fields, or date fields, date shifting, and hashing of the record names. It also includes a randomization module. REDCap utilizes a third-party vendor, Twilio, to send an SMS message with a REDCap survey link. Subjects can click on the link and be directed to a REDCap survey on their phone.

During all phases of a study, we aim to ensure that all data are carefully measured and recorded. We will use prepared phone scripts for recruitment, appointment reminders, and weekly check-in calls to provide information about the study and its procedures and to obtain study responses in as consistent a manner as possible. Our manual of operations will include details on where to obtain patient information, how to record the data, how to classify and report adverse events, and whom to contact with questions so that all members of the study team record information in a consistent manner throughout the trial.

All study staff will be trained and certified in privacy protection, the Health Insurance Portability and Accountability Act (HIPAA), and the ethical conduct of clinical research. Study team members will meet regularly for study training and to make sure that all questions are asked similarly.

We will check the consent form and any paper forms for completeness, and double-enter the data to minimize errors.

Our REDCap database will have data validation rules and required fields to minimize the risk of incorrect and missing information. To ensure that the data are accurate and complete, we will create study-specific flow sheets for each study visit to ensure that the data collected is consistent at each study visit. Prior to initiating the study, the PI or her designee will hold a session to train Clinical Research Center staff in the conduct of the study. The study team will enter data in real time directly into the REDCap database rather than completing paper forms and manual data entry. This includes baseline information such as inclusion and exclusion criteria, randomization arm, measures of adherence to the drinking and washout periods, visit data such as vital signs and blood draw details, medication changes, adverse events, and other measures.

We will use standardized procedures for measuring vital signs and obtaining blood samples, and we will use validated measures for assessing the frequency of alcohol intake to increase the likelihood that the data is accurate and complete.

We will call participants once a week to make sure that they have access to their drinks, that they are adhering to the protocol, and that they complete the study assessments.

Quest Diagnostics will conduct specimen analyses for safety markers (hepatic panel, complete blood count with differential, fasting basic metabolic panel, and lipid panel). We will follow standard laboratory practices regarding sample chain of custody and sample confidentiality. This lab is approved by the Harvard Catalyst organization, and it is used by the BIDMC Clinical Research Center because they provide high-quality research and clinical data.

We will label all specimens with the date and time of the blood draw and two subject identifiers using labels from the Quest Diagnostics ordering system to minimize the risk of mislabeling specimens. We will send the samples for safety monitoring assays to Quest Diagnostics within 72 hours of collection. Prior to transport to the Quest Diagnostics laboratory, samples will be processed according to the laboratory guidelines for sample submission.

We will obtain laboratory results about the safety measures from the Quest eResults system and manually enter the data into the study database. We will retain paper copies of the reports and periodically conduct audits to compare the entered data with the paper copies to ensure that it was accurately entered in the study database.

The Brigham Research Assay Core (BRAC) will conduct specimen analyses for sex hormones. We will centrifuge the samples for sex hormone assays and freeze the serum in aliquots at -80°C. At the end of the study, we will bring the samples to the BRAC. They will use liquid chromatography–mass spectrometry to measure estradiol, estrone, and testosterone, and they will use chemiluminescence to measure sex hormone binding globulin (SHBG) and dehydroepiandrosterone sulfate (DHEAS). We will follow their sampling, storage, and transport procedures.

We will obtain laboratory results about the sex hormone measures from the Freezerworks database on the BRAC web portal system and manually enter the data into the study database. We will retain paper copies of the reports and periodically conduct audits to compare the entered data with the paper copies to ensure that it was accurately entered in the study database.

Only members of the research team, including the CRC nurses, will have access to the data and specimens. Quest Diagnostics will transmit results through their secure

eResults system with study-specific account access. We will download results and enter the data into our study-specific REDCap database.

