1.0 Objectives*

Alcohol intake raises sex hormone levels, however, it is unknown if that effect persists in postmenopausal women with estrogen receptor-positive (ER+) breast cancer on aromatase inhibitor (AI) therapy, which is an estrogen suppressant. There have been no studies to examine alcohol's effect on sex hormone levels among postmenopausal women with ER+ breast cancer receiving AI therapy. These drugs are only prescribed to postmenopausal women who had ER+ breast cancer, the subtype where alcohol has been found to increase breast cancer incidence. This information is needed for postmenopausal women with estrogen receptor-positive (ER+) breast cancer to make informed decisions about their alcohol intake and its potential effect on adjuvant AI therapy.

To address this issue, we will conduct a pilot randomized controlled crossover trial of 20 postmenopausal women with estrogen receptor-positive (ER+) breast cancer who receive AI therapy and who consume at least one alcoholic drink per week but not more than one drink per day, to assess whether alcohol at low "real-world" levels of intake increases sex hormone levels in the presence of AI's.

We hypothesize that the expected within-person increases in sex hormone levels following light alcohol consumption will not be observed among women using aromatase inhibitor therapy throughout study enrollment.

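### The primary endpoint divides a drug-suppressed hormone by SHBG, but the plan gives no assay limit and no valid way to analyse estradiol results below one

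*Combined protocol and SAP*

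**What the plan says.** Section 1.0 describes "aromatase inhibitor (AI) therapy, which is an estrogen suppressant" and hypothesises that the expected hormone increases "will not be observed among women using aromatase inhibitor therapy throughout study enrollment". Section 3.0 requires every participant to be on such a drug.

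Section 11.0 states: "Our primary endpoint is free estradiol (estradiol divided by SHBG"). The model is a linear mixed model "including a random subject intercept and fixed effects for treatment and sequence". On scale it says "We will use a logarithmic transformation for skewed distributions of the sex hormone levels". On missing data it says "We will use Markov Chain Monte Carlo (MCMC) multiple imputation", done for each treatment arm with a SAS "procedure to generate 10 multiply imputed datasets".

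For the assay, Section 11.0 names liquid chromatography–mass spectrometry "to measure estradiol, estrone, and testosterone". Neither that section nor any other gives a detection or quantification limit, an expected estradiol level on treatment, an expected share of results below the limit, or a rule for handling them.

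**The concern.** The numerator of the primary endpoint is the hormone that the background drug is meant to suppress, so some results may come back as less than a limit. Such a result is known to be low, but its value is unknown. It cannot be logged or divided by SHBG without a further rule.

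Section 11.0 says that results are entered by hand into a database with validation rules and required fields, and Section 24.0 mentions data-type checks. A text result would therefore probably become either a blank or a substituted number. A blank would go to the imputation, which assumes that values are missing at random given the observed data. Here they are absent because they are low. A substituted number brings a bias that depends on the constant chosen, and the plan chooses none.

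The direction matters because the trial expects to see no rise and means to inform women's decisions about alcohol. Shrinkage or lost power could be read as evidence that the drug blocks the effect.

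**Working it through.** **The plan's own figures.** With 20 women, a two-sided 0.05 level and a t test on 18 degrees of freedom (noncentrality δ√20/SD), the minimum detectable differences at 50/80/90% power are 19.4/27.8/32.2% for SD 42% and 6.0/8.6/10.0% for SD 13%. These round to all six figures in Section 11.0. They concern estrone sulfate and DHEAS; the section gives none for estradiol or the ratio.

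**Inputs.**
- True rise 22%: the top of the postmenopausal estrone sulfate range in Section 11.0, borrowed for estradiol.
- SD of within-woman log differences 0.42: borrowed from the 42% for estrone sulfate.
- Between-woman SD of log estradiol 0.6: an assumption.
- Share of juice-phase values below the limit 10, 25, 50 or 70%: an assumption.

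On the log scale the rise is δ = ln 1.22 = 0.1989. The SD of a single value is s = √(0.6² + 0.42²/2) = √0.4482 = 0.6695. If a share p of juice values is below the limit, put z = Φ⁻¹(p) and z′ = z − δ/s = z − 0.297. The limit is L = s·z, with juice values centred at zero.

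**Blank and imputed per arm.** Univariate imputation reproduces, on average, the mean of the detected values in each arm:
- Juice: s·φ(z)/(1 − Φ(z)).
- Wine: δ + s·φ(z′)/(1 − Φ(z′)).

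At 10%: 0.2803 − 0.1305 = 0.1498, a rise of 16.2%. At 50%: 0.6132 − 0.5342 = 0.0790, a rise of 8.2%. (A simulation of the 50% case gave about 7%.)

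**Constant substituted.** With f × limit, each arm's mean is (share below) × (L + ln f) + (share detected) × (detected mean). At 50%, L = 0 and 38.3% of wine values are below the limit:
- Juice: 0.5 ln f + 0.5 × 0.5342 = 0.5 ln f + 0.2671.
- Wine: 0.3832 ln f + 0.6168 × 0.6132 = 0.3832 ln f + 0.3782.
- Difference: 0.1111 − 0.1168 ln f.

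This gives 11.8% for f = 1, 21.2% for f = 1/2 and 46.2% for f = 1/10.

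**Average estimated rise (truth 22%).** The last column is a simulation of 600 trials of 20 women, fitting a left-censored random-intercept model with a treatment effect. Its Monte Carlo error is 0.4 to 0.6 points.

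| Juice values below limit | Imputed per arm | Limit | Limit/√2 | Limit/2 | Limit/10 | Censored model |
|---|---|---|---|---|---|---|
| 10% | 16.2% | 20.1% | 21.9% | 23.8% | 32.6% | 21.4% |
| 25% | 12.2% | 17.1% | 20.6% | 24.2% | 42.2% | 21.5% |
| 50% | 8.2% | 11.8% | 16.4% | 21.2% | 46.2% | 21.6% |
| 70% | 5.9% | 7.3% | 11.5% | 15.8% | 38.2% | 21.4% |

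**Power.** With complete data, power for the 22% rise is 52% in simulation. With 50% below the limit it is 34% (limit), 38% (limit/√2), 36% (limit/2) and 28% (limit/10). With 10% below it is 49, 50, 48 and 38%.

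**The ratio.** Section 2.0 says that alcohol raises SHBG but gives no size. Assume 5% (ln 1.05 = 0.0488), unrelated to estradiol. The true ratio change is 1.22/1.05 − 1 = 16.2%. At 50% below the limit, per-arm imputation gives exp(0.0790 − 0.0488) − 1 = 3.1%, and substituting the limit gives exp(0.1111 − 0.0488) − 1 = 6.4%. About 33% of pairs are then below the limit in both phases. With a constant numerator, the ratio in those pairs moves only with SHBG.

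A censored model for log(estradiol/SHBG), with each sample's censoring point at log(limit) − log(SHBG), gave 15.8, 16.2, 17.1 and 18.2% at the four shares (assumed SD of log SHBG 0.4 between women, 0.1 within). The censored estradiol effect minus the observed SHBG effect gave 15.6, 15.6, 15.8 and 15.6%. The upward drift of the ratio model at high shares arises because SHBG enters both the outcome and its censoring point.

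**The case against.** The strongest reply is that the plan never says that results below the limit count as missing. Section 11.0 offers imputation for missing values; that such results would end up there is an inference from the data-entry rules. This stands. A reader might infer that the log transform, the ratio and the imputation together must shrink a real rise. The documents do not support that. The log and the ratio do not attenuate by themselves. The unstated handling rule sets the direction, and the table shows overstatement with limit/2 at low shares and with limit/10 throughout.

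The imputation figures are also a simple case. Section 11.0 does not list the imputation variables, and estrone, testosterone, DHEAS and SHBG are measured at all four visits. A richer imputation could do better. A likelihood that uses both of a woman's phases but still treats the low values as missing at random gave 19, 17, 13 and 10% at the four shares. That is milder, but still too low.

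Finally, suppressed does not mean undetectable. The assay may be sensitive enough for few or no results to fall below its limit. This also stands, and it is why the size is given as a range. It does not remove the need for a rule on the numerator of the primary endpoint.

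**Conclusion.** The point holds as a gap with a concrete better method. The primary endpoint rests on estradiol in women on an estrogen suppressant, and the stated model and imputation cannot correctly use a result below the limit.

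If such results are imputed per arm as missing, the bias is toward the hypothesised null: from 22% to about 16% with a tenth of juice values below the limit, and to about 7 to 8% with half. If a constant is substituted, the bias may go either way. In these runs every constant lost power, and the loss was large when half the values were below.

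The figures rest on a rise and an SD borrowed from estrone sulfate, an assumed between-woman SD and assumed shares below the limit. The true share is not in the documents, so the effect may be negligible or severe. A reader might also infer that a null result from this trial would be an assay artefact; nothing in the documents shows that.

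**What to change.** Sections 9.0 and 11.0 place the hormone assays at the end of the study, so the rule can be fixed before any result exists:

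- Define estradiol results below the limit as left-censored, not missing, and keep them out of PROC MI.
- Fit a censored (Tobit-type) mixed model with a random subject intercept and the planned treatment and sequence effects, for example in PROC NLMIXED. Apply it to log(estradiol/SHBG), with each sample's censoring point at log(limit) − log(SHBG), and to log estradiol.
- As a check, report the log estradiol effect minus the log SHBG effect. If many values are censored and the two disagree, rely on the subtraction, for the reason given in the working.
- Obtain the limit, and any numeric readings below it, from the laboratory that runs the assay. Section 9.0 (Blood Samples) names Quest Diagnostics for the sex hormones and Section 11.0 names the Brigham core, so this needs settling first.
- Report the share below the limit by phase, and add a sensitivity analysis over substitution constants.

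Switching to a rank or sign test when more than half the values are below the limit is not advised. Pairs below the limit in both phases are ties (about 33% of pairs at a 50% share and 54% at 70%), while the censored estradiol model stayed close to the truth at both.

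The cost is a paragraph of text and one extra model type. Intervals widen if most values are censored. In the simulation the standard error of the log estradiol effect was 0.112 at 50% and 0.141 at 70%, against 0.42/√20 = 0.094 with complete data, so about 19% and 50% wider.
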